Qsymia provides a potential opportunity to develop an effective treatment plan that would be an adjunct to surgical intervention in the super obese patient. Use of Qsymia in addition to a low-calorie dietary prescription pre-operatively would effectively decrease weight prior to surgical intervention, lowering surgical risk to some extent. Additionally, if continued post-operatively, Qsymia as an adjunct to the post-surgical dietary plan would potentially extend the weight loss horizon so that the probability of the typical weight loss plateau at 12-18 months is decreased. The combination of the pre-operative and post-operative weight loss associated with Qsymia use could significantly diminish the need for a second surgical procedure in super obese patients. We have designed a pilot study to examine the use of Qsymia in super obese patients to determine its potential for decreasing the need for a second weight loss surgery.

Primary Objective

The primary objective of the proposed study is to demonstrate the effectiveness of using Qsymia in the superobese (BMI ≥ 50 kg/m²) as an adjunct to surgical therapy.

Secondary Objectives

Secondary objectives of the proposed study include determining tolerability of Qsymia perioperatively, determining changes in resting metabolic rate postoperatively (3 months and 12 months post-surgery), determining the magnitude of preoperative weight loss and determining the magnitude of weight loss at 12, 18, and 24 months post-surgery.

Treatment Plan

Treatment Group

Patients with a BMI ≥ 50 kg/m² that agree to participate in the experimental group will begin their treatment plan with a medical weight loss diet that includes a low-calorie diet and Qsymia at the recommended treatment dose of 7.5/46 mg daily (following initiation of the titration dose for 2 weeks). The low-calorie diet will be individually tailored based on initial resting metabolic rate measurement and co-morbid conditions. Patients will be medically monitored with once monthly medical visits and also have once monthly visits with a dietitian to review the treatment plan. Patients will receive medical weight loss therapy for a minimum of 3 months prior to proceeding to the laparoscopic sleeve gastrectomy. If a patient opts not to proceed to sleeve gastrectomy, they will continue to receive medical therapy for weight reduction including Qsymia and followed for the duration of the study (i.e., for 2 years).

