Patients will discontinue Qsymia the week prior to the scheduled operation. The sleeve gastrectomy will be performed by one of the surgeons at the Weight Management Center ([name], [name], [name]) using standard laparoscopic technique. Post-operatively, all patients will be provided with dietary counseling and a nutrition prescription for a very low calorie, high protein diet: 500-700 calories, protein goal of 1-1.2g/kg IBW, and 60-75g carbohydrate. Qsymia will be resumed in the second post-operative week at the initial titration dose and increased to the recommended treatment dose of 7.5/46 mg daily. Patients will have standard post-operative surgical follow up at months 1, 3, 6, 9, 12, 18, and 24. During the post-operative phase, all patients will be enrolled in the bariatric support group program that meets on a monthly basis. Patients will also have at least 3 visits with a clinic dietitian to review and update dietary prescriptions. At any point during this course of follow up, a determination can be made that the primary outcome event has occurred if the patient has a weight plateau—defined as weight gain or < 3 lbs weight loss—for 3 consecutive months, remains above a BMI of 39.9 kg/m² and continues to have associated co-morbidities. These patients will be evaluated for the possibility of moving forward to the next operative stage (laparoscopic Roux-en-Y gastric bypass) while all other patients will continue on with medication and diet/exercise therapy.

Control Group

Control subjects for the proposed study will be identified from the patient population at the Wake Forest Baptist Health Weight Management Center. They will be matched to subjects in the treatment group on age, sex, ethnicity, and BMI. They will be a historical control group who had surgery prior to the commencement of the proposed study (retrospective review).

Trial Design

Prospective independent historical case control

Inclusion Criteria

Inclusion criteria for the proposed study are:

- BMI \geq 50 kg/m²
- Determined to be a good candidate for surgery based on medical and psychological exam.
- Willing to participate in a 3-6 month medically supervised weight loss plan prior to surgery.
- Planning to remain in the reasonable vicinity of the Wake Forest Baptist Health Weight Management Center for the duration of the study.

Exclusion Criteria

- History of prior weight loss surgery (removal/conversion from band to sleeve will not be excluded)

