- Pregnant (women of childbearing potential will complete a pregnancy test (blood draw) to make sure they are not pregnant at the time that they initiate the medication). Ongoing monitoring of pregnancy status is the responsibility of the patient and they are instructed as such in the consent form.
- Ongoing use of weight loss medication
- Contraindications to use of Qsymia, including pregnancy, history of glaucoma, unstable cardiac disease (unstable angina, recent heart attack or stroke (in the past 6 months), uncontrolled arrhythmia), hyperthyroidism, taking MAOIs (monoamine oxidase inhibitors) or allergy to either topiramate or sympathomimetic amines like phentermine.

Patients may be removed from the study at any point if they are unable to tolerate the study medication or are less than 50% compliant with the study medication (take less than 50% of the recommended dose). If a patient is removed from the study due to medication intolerance or non-compliance, the study physician will meet with them and instruct them on how to stop the medication.

Primary endpoint

The primary endpoint for this study is the proportion of patients that meet the criteria to move forward with the second surgical procedure (Roux en Y Gastric Bypass). The criteria include all of the following at any point in the 24 month post-surgical follow up period:

1. Weight plateau (defined as weight gain or < 3 lbs weight loss) for at least 3 months
2. Remains above a BMI of 39.9 kg/m²
3. Continues to have obesity associated co-morbidities (Co-morbidities include hypertension, type 2 diabetes mellitus or pre-diabetes, hyperlipidemia, metabolic syndrome, obstructive sleep apnea, osteoarthritis, non-alcoholic steatohepatitis (NASH), gastroesophageal reflux disease (GERD)).

We hypothesize that the study group treated with Qsymia plus surgery will have a lower rate of occurrence of the primary endpoint at 24 months post-surgery compared to the group with surgery only.

Secondary endpoints

The secondary endpoints for this study are percent weight loss both before and after surgery and changes in percent body fat and resting metabolic rate.

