This is an independent case-control study. Analyses will include completers only. Completers are defined as individuals who enter treatment and continue it (Qsymia and/or gastric sleeve) for at least 24 months without reversal or discontinuation. Participants will be recruited until the sample size of 20 cases is obtained. If a participant consents but does not have surgery, this person will not be counted as a case and thus, recruitment will continue.

Data will be entered into and stored in a REDCap database with access given only to individuals who are part of the study team. Study data uploaded will include information from the weekly clinic questionnaire, adverse events, as well as study outcomes (weight at clinic visits), demographic information, etc.

[figure not shown]
Most of the statistical analyses will be conducted using SPSS or SAS. Prior to testing the specific aims, descriptive statistics will be used to characterize the sample. Next, the groups will be compared using the chi-square statistic and T-test statistic to determine whether differences existed between the groups on key variables that may have an effect on outcomes. The case-control matching procedure should insure balance between the treatment groups on sex, age, BMI and ethnicity, but additional analyses will be used to examine the comparability between groups on baseline body composition, waist circumference, and resting metabolic rate.

The primary endpoint for this study is the proportion of patients that meet the criteria to move forward with the second surgical procedure (Roux en Y Gastric Bypass) at any point during follow up. The proportion of the Qsymia treated group that achieves the primary endpoint will be compared to the surgery only group after 24 months of follow up. Unadjusted and adjusted models will be developed to test for differences in the rate of the primary endpoint occurrence by treatment group.

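### The completer rule counts 24 months from entry to treatment but the primary endpoint counts 24 months from surgery, so a Qsymia patient who leaves late can be analysed without a full endpoint window

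*Combined protocol and SAP*

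**What the plan says.** Two clocks are in use.

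- **Who is analysed.** The Statistical analysis section says "Analyses will include completers only" and defines them as "individuals who enter treatment and continue it (Qsymia and/or gastric sleeve) for at least 24 months without reversal or discontinuation". The count starts on entering treatment; surgery is not named as its origin.
- **What is scored.** The Primary endpoint section says "The criteria include all of the following at any point in the 24 month post-surgical follow up period". The hypothesis in that section is also set at 24 months after surgery, for both groups.

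For Qsymia patients these origins differ. Under Treatment Group, participants "will begin their treatment plan with a medical weight loss diet that includes a low-calorie diet and Qsymia", and "Patients will receive medical weight loss therapy for a minimum of 3 months prior to proceeding to the laparoscopic sleeve gastrectomy". That sentence gives no maximum. The inclusion criteria give a range: "Willing to participate in a 3-6 month medically supervised weight loss plan prior to surgery". Controls are historical surgical patients with no Qsymia lead-in.

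The post-operative schedule under Treatment Group runs to month 24, with no visit between months 18 and 24. The Safety Monitoring section adds a month 15 visit but nothing after month 18 except month 24. The Statistical analysis section restates the endpoint as occurring at any point in follow-up, compared after 24 months of follow-up, and does not repeat that the period is post-surgical.

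**The concern.** The endpoint is of the ever-met type, so a patient observed for less time has less chance of being counted. With such an endpoint, the rule that admits patients to the analysis should guarantee the full observation window. Here it does not. A Qsymia patient with a 5-month lead-in who leaves at post-operative month 19 has had 24 months of treatment and qualifies as a completer, although the last 5 months of the endpoint window were never observed. The plan has no rule for a missing outcome, so the natural default is to score that patient as not having met the criteria.

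The lead-in exists only in the Qsymia group, so a shortfall arising this way can only lower the Qsymia event proportion. That is the direction the study hopes to show.

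**Working it through.** **The plan's own figure.** Inputs from the sample size section: event rates 0.70 (control) and 0.25 (Qsymia), uncorrected chi-squared, alpha 0.05 (two-sided assumed). With 20 per group, the pooled rate is (0.25 + 0.70)/2 = 0.475, and

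z = [0.45 − 1.96·√(2·0.475·0.525/20)] / √[(0.25·0.75 + 0.70·0.30)/20] = (0.45 − 0.3095)/0.1410 = 0.997, so power = 0.8405.

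This matches the stated .840. The 25 versus 20 printed beside it gives 0.880. I therefore use 20 versus 20 below, which also agrees with the 20 cases in the Statistical analysis section.

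**Post-operative time guaranteed by the completer rule.**

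| | Lead-in (months) | Post-operative month at which 24 months of treatment is reached |
|---|---|---|
| Qsymia, shortest lead-in | 3 | 24 − 3 = 21 |
| Qsymia, longest lead-in in the inclusion criteria | 6 | 24 − 6 = 18 |
| Control | 0 | 24 |

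A lead-in longer than 6 months would widen the gap. Anyone leaving between months 18 and 24 has month 18 as the last scheduled visit, so the final 6 months of the window are lost (6/24 = 25%).

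**Loss per affected patient.** The documents do not give the timing of events, so I take two assumed shapes, each with a true 24-month rate of 0.70 in both groups (no treatment effect):

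- Events spread evenly over months 6-24: 0.70 × 6/18 = 0.233.
- Constant hazard from surgery: the rate by month 18 is 1 − 0.30^(18/24) = 0.595, so the loss is 0.70 − 0.595 = 0.105.

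**Bias in the Qsymia proportion.** Assume that 10-20% of treated patients (2-4 of 20) leave in this interval, are kept as completers, and are scored as not met:

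- Even spread: 0.10 × 0.233 = 0.023 to 0.20 × 0.233 = 0.047, or about 2-5 points.
- Constant hazard: 0.10 × 0.105 = 0.011 to 0.20 × 0.105 = 0.021, or about 1-2 points.

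With 20 treated patients, even 4 affected under the even spread means 4 × 0.233 = 0.93 of one expected event.

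**Effect on the test.** Exact enumeration of the uncorrected chi-squared at 20 versus 20, control rate 0.70, even spread:

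| Qsymia rate as scored | Two-sided rejection | Rejection favouring Qsymia |
|---|---|---|
| 0.700 (no bias) | 5.3% | 2.7% |
| 0.677 (10% affected) | 5.6% | 3.8% |
| 0.653 (20% affected) | 6.5% | 5.3% |

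**The case against.** The strongest reply is that the outcome window is already fixed. The endpoint is defined "at any point in the 24 month post-surgical follow up period", the hypothesis is set at the same point for both groups, and visits are scheduled to month 24. The completer rule selects patients; it does not end observation, and nothing says that scoring stops once completer status is reached. This stands, and it limits the problem to patients who actually leave between about months 18-21 and 24. It does not remove the problem, because a defined window cannot supply data on someone who has gone.

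The wording also allows a second reading, in which a patient given both treatments must continue both for 24 months. The sleeve would then need 24 post-operative months in either group. That is possible, and the text does not settle it, which is itself a reason to state the origin.

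The asymmetry with controls is partly inferred. The rule speaks of continued treatment, not continued records, so a control with an unreversed sleeve whose chart ends at month 19 might be kept rather than dropped. The documents do not say which. What is certain is only that a control has no pre-operative treatment time to count.

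A reader might go further and infer that operated patients are followed for only two years from entry, because the Treatment Group text says "followed for the duration of the study (i.e., for 2 years". That clause concerns patients who opt not to have the sleeve, and the Statistical analysis section does not count them as cases. Stopping every Qsymia patient at post-operative month 18 would, with the even spread, set 0.467 against 0.70 and reject about 31% of the time at 20 versus 20. The schedule and the endpoint definition contradict that scenario, so the figure is not a measure of this defect.

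Finally, the rationale places the typical plateau at 12-18 months. This may mean fewer first events after month 18 than the even spread assumes, so the lower end of the range may be nearer the truth.

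**Conclusion.** The completer rule is tied to the wrong origin for this endpoint. Read literally, it admits Qsymia patients with as little as 18-21 post-operative months to an analysis whose endpoint needs 24. This is a mismatch between two stated rules, not a demonstrated bias in the trial.

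The likely effect is small: about 2-5 points in the Qsymia proportion under the even spread, or 1-2 points under a constant hazard. The corresponding rise in two-sided rejection under the even spread is from 5.3% to 5.6-6.5%. These figures rest on four assumptions that the documents do not supply: the shape of event timing, a 10-20% share of late leavers, scoring those leavers as not met, and a full window for every control. Because the rule governs the primary analysis set and this route to error runs in the direction of the hypothesis, it is worth correcting despite its size.

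**What to change.** In the Statistical analysis section, define the completer's 24 months as running from sleeve gastrectomy in both groups, and require outcome follow-up through post-operative month 24 in both. State that a patient who met all the endpoint criteria before leaving is kept and counted as an event. Without that clause, the stricter rule would discard observed events.

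The cost is a sentence or two of text. A few late leavers without an event lose completer status. The power inputs do not change. Keeping leavers who had an event while dropping those who had not can raise a group's event proportion somewhat. The rule should therefore be identical in both groups, and the number of late leavers in each should be reported, with a sensitivity analysis that counts the excluded ones first all as non-events and then all as events.

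### Pre-operative weight loss is to be estimated only in operated completers, a group fixed after at least 3 months of Qsymia; it should also be estimated in all starters, with those who do not reach surgery accounted for

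*Combined protocol and SAP*

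**What the plan says.** - **Target and replacement (Statistical analysis).** "Participants will be recruited until the sample size of 20 cases is obtained". Then: "If a participant consents but does not have surgery, this person will not be counted as a case and thus, recruitment will continue".
- **Analysis set (same section).** "Analyses will include completers only". Completers are those who enter treatment and "continue it (Qsymia and/or gastric sleeve) for at least 24 months without reversal or discontinuation".
- **Order of events (Treatment Plan, Treatment Group).** "Patients will receive medical weight loss therapy for a minimum of 3 months prior to proceeding to the laparoscopic sleeve gastrectomy". That therapy is diet plus Qsymia.
- **Patients who decline surgery (same section).** "If a patient opts not to proceed to sleeve gastrectomy, they will continue to receive medical therapy for weight reduction including Qsymia", with follow-up for 2 years.
- **Removal (after the Exclusion Criteria).** Patients may be taken off study if they cannot tolerate the drug or take less than half of it.
- **The outcome.** Secondary Objectives include "determining the magnitude of preoperative weight loss". The analysis text compares percent weight loss between groups by t-test, and its first window runs from baseline to surgery.
- **Primary endpoint.** It is assessed during the 24 months after surgery, against historical controls who all had surgery.
- **Safety Monitoring.** Adverse-event frequencies are reported for those on study drug, and blood chemistry derangements for all participants.

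**The concern.** Pre-operative weight loss on Qsymia is complete before the sleeve operation takes place, so it can be observed in everyone who starts the drug. The plan nevertheless counts only starters who go on to surgery, and then only those who meet a 24-month continuation rule. Both conditions come after the outcome.

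The documents give routes by which experience on the drug could influence whether a starter meets them: the patient may opt out of surgery, or may be removed for intolerance or poor adherence. If those who leave lost less weight than those who stay, the operated cases overstate the pre-operative effect. If they lost more, and for that reason saw less need for an operation, the operated cases understate it.

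At stake is a secondary objective of a pilot study. A clinician considering Qsymia before surgery needs the weight loss to expect when starting the drug, and the chance that a starter reaches the operation. The plan describes no efficacy estimate in all starters and makes no commitment to report how many were replaced to reach 20 cases.

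**Working it through.** **1. The plan's own figures.** The documents state no non-surgery rate, no dropout rate and no SD for weight loss, so there is no planned figure for this outcome to reproduce. The nearest is the sample-size statement: 25 experimental and 20 control subjects, failure rates 0.25 and 0.70, alpha 0.05, uncorrected chi-squared test, power .840. The two-sided normal approximation is

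power = Φ[(|p1 − p2| − 1.96·se0)/se1], with se0 from the pooled rate and se1 from the separate rates.

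- 25 v 20: pooled rate 0.45, se0 = √(0.45·0.55·(1/25 + 1/20)) = 0.1492, se1 = √(0.1875/25 + 0.21/20) = 0.1342. Power = Φ[(0.45 − 0.2925)/0.1342] = 0.880.
- 20 v 20: pooled rate 0.475, se0 = 0.1579, se1 = 0.1410. Power = Φ[(0.45 − 0.3095)/0.1410] = 0.8405.

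The stated power therefore fits 20 v 20. The plan does not say that the gap between 25 and 20 is an allowance for starters who do not reach surgery, so it cannot be used as a non-surgery rate. Nothing below depends on this figure.

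**2. Timing.** In order: baseline weight and start of Qsymia; at least 3 months of treatment, over which pre-operative loss accrues; surgery or no surgery, which decides case status; then 24 months of continuation, which decides completer status. Both selection steps come after the drug has been taken, and the second may come up to two years after the outcome was complete.

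**3. Possible shift in the mean (illustration).** Let a share s of starters not reach surgery; s is assumed, with a range of 10% to 30%. Take weight loss as normal. At the extremes, those missing are exactly the poorest or exactly the best responders. The operated mean then differs from the all-starter mean by

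shift = φ(z_s)/(1 − s) SD, where Φ(z_s) = s.

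| s (assumed) | shift if poorest or best responders are missing | starters needed for 20 operated cases, 20/(1 − s), rounded up |
|---|---|---|
| 10% | ±0.20 SD | 23 |
| 20% | ±0.35 SD | 25 |
| 30% | ±0.50 SD | 29 |

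The shift is upward if the poorest responders are missing and downward if the best are. If non-surgery is unrelated to weight loss, it is zero. These are outer limits for each s under normality. Without an SD in the documents they cannot be turned into percent weight loss.

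**4. Internal wording.** The phrase about continuing "continue it (Qsymia and/or gastric sleeve) for at least 24 months without reversal or discontinuation" can be read so that a non-operated patient who stays on Qsymia for 24 months is a completer. The replacement rule says that the same person is not a case. The text does not settle whether such a patient enters any efficacy analysis.

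**The case against.** **The primary endpoint makes restriction to operated patients natural.** It is eligibility for a second operation, assessed after the first, and every control was operated on. This stands. A reader might infer that the primary rate is invalid because non-operated starters are left out. The documents do not support that: the endpoint is not defined for someone who had no sleeve gastrectomy. What remains is a limit of scope. Cases passed through a Qsymia phase before surgery and controls did not, so the result applies to starters who reach surgery.

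**Recoding non-proceeders is weak evidence of harm.** With five assumed non-proceeders and the planned rates, the uncorrected chi-square gives p = 0.0044 for 5/20 v 14/20, p = 0.0007 for 5/25 v 14/20 (all five non-events) and p = 0.045 for 10/25 v 14/20 (all five events). All stay below 0.05. A sixth counted as an event would give 11/26 v 14/20, p = 0.062, so the outcome turns on an invented count. The exercise also adds non-operated patients to one arm only, and none of these p-values concerns pre-operative weight loss.

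**Selection on response is not documented.** A reader might infer that surgery is offered or withheld according to response to the drug. No section says so. The text shows selection after exposure, with routes that may relate to drug experience.

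**Non-proceeders are not excluded from everything.** A reader might infer that they are. Safety Monitoring covers those on study drug and, for chemistries, all participants, and the completer wording is ambiguous.

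**Not all non-proceeders are followed.** The 2-year follow-up is promised to those who opt out of surgery. Those removed for intolerance or non-compliance may have no later weights. This stands and limits the fix.

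**An all-starter estimate has no counterpart among the controls.** This also stands, so it can only be a single-arm description beside the planned comparison.

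**Conclusion.** The point holds for the pre-operative weight-loss objective and for the accounting of starters who do not reach surgery. Followed as written, the plan estimates a pre-surgical outcome in a subset fixed after drug exposure, and it does not commit to showing how large the remainder is.

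The direction and size of the bias cannot be determined from the documents. The limits of about ±0.20 to ±0.50 SD rest on an assumed 10% to 30% non-surgery share, a normal distribution and the most extreme selection; the true shift could be zero. The replacement rule also covers people who consent but never start Qsymia. Replacing them does not affect an estimate among starters.

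The point does not overturn the primary comparison. It calls for a modest addition to a secondary, exploratory analysis and a clear statement of whom the primary result describes.

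**What to change.** 1. Add a single-arm estimate of pre-operative weight loss, with a confidence interval, in all participants who start Qsymia. Use one fixed time, for example the month-3 monthly visit, with the last available weight for those who stop earlier, and report how many values were carried forward. Keep the planned baseline-to-surgery comparison of operated cases and controls beside it.
2. Report the number who consented, started Qsymia, reached surgery and were replaced to obtain 20 cases, with reasons for not proceeding.
3. Reconcile the completer definition with the rule that a non-operated participant is not a case, and say which analyses each group enters.
4. Keep the primary comparison in operated patients and state that it applies only to starters who reach surgery. Any bounding that codes non-proceeders as events or non-events is optional and exploratory. It would also have to be squared with the side-effect monitoring text, which treats some medication withdrawals as the endpoint being reached.

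The cost is SAP wording and one extra analysis set. Monthly pre-operative visits are already planned, weight is taken at every clinic visit, and clinic weights are to be entered in the study database, so no new visits are needed. The downside is incomplete weights for participants removed from the study.
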